 - b. The number of available and eligible potential participants and rates of recruitment

- c. The willingness of participants to be randomised
 - d. The appropriateness of the proposed set of outcome measures
 - e. Rates of adherence and compliance to follow-up assessments
 - f. The time required to collect and analyse data
3. Provide an initial estimate of the extent to which the two eHealth interventions maintain benefits from memory rehabilitation compared with no active maintenance, measured over an 18-week period; and
 4. Estimate the potential cost and cost-effectiveness of delivering the proposed maintenance intervention program (i.e. booster sessions and SMS reminders) compared with no active maintenance.

Ultimately, we will use the information from all four of these aims to estimate the parameters for a Phase III trial.

Hypotheses

We hypothesise that the level of everyday memory function at the end of the study, from largest to smallest effect, will be: eHealth booster sessions > SMS/Email reminders > no active maintenance.

STUDY DESIGN

Research Design

We will conduct a multi-site, single-blind, Phase II pilot randomised controlled trial (RCT) with three arms to evaluate two eHealth interventions designed to sustain the effects of memory skills training (booster sessions delivered via videoconferencing, and SMS/email reminders) compared to no active maintenance. We will use an intention to treat method of analysis, as well evaluate the maintenance interventions as per protocol in terms of:

- 1) Feasibility;
- 2) Effectiveness in prolonging intervention-related gains; and
- 3) Estimated cost.

PARTICIPANTS

Recruitment Procedure

Potential participants will be identified from survivors of stroke enrolled to participate in a memory skills group program at one of the health service sites participating in the study (please see Study Sites section). These sites are already running, or are planning to run, memory skills groups as part of usual care.

Recruitment will follow a two-step process:

1. Prior to commencing the memory skills group program, willingness to participate in the Memory-SuSTAIN study will be established. Health service staff will obtain verbal consent for identified potential Memory-SuSTAIN participants to be contacted by study staff to discuss participation.

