- Pairwise comparisons and linear mixed models will be used to explore between-group differences at T3 and T4 in acceptability ratings. Qualitative data will be thematically analysed to extract themes relating to intervention acceptability from participant interviews, using Braun and Clarke's (2006) approach to thematic analysis.

Aim 2 (*Determining whether the trial design is feasible*)

- Descriptive statistics will be calculated for feasibility measures, including rates of recruitment, study completion, and technological issues.

Aim 3 (*Determining an initial estimate of intervention-effectiveness*):

- Pairwise comparisons and linear mixed models will be used to explore between-group differences at each time point in clinical outcomes. The effect size of each maintenance condition, defined as the magnitude of change from T1-T4, will be estimated with Cohen's *d* based on output from regression models.

Aim 4 (*Estimating and comparing costs of booster sessions, SMS/email reminders, and no active maintenance*):

- Resource use data will be converted to costs and the average costs per participant for each intervention arm described and compared. The costs of each program will be accounted for in the determination of total costs and the average cost per participant. The reference year for costs will be 2019. The net cost per participant achieving the maintenance outcome will be estimated against the control group as a measure of potential cost-effectiveness. Various sensitivity analyses will be performed. If effectiveness information is able to be used for health benefit modeling relative to costs, then these will also be described to inform the business case and budget needed for a larger, fully powered Phase III study.

REPORTING OF RESULTS

Study results will be prepared for publishing at the completion of data collection and analysis. Results will be reported according to guidelines outlined by the Consolidated Standards of Reporting Trials (CONSORT) extension for randomised pilot and feasibility trials checklist, and the Template for Interventional Description and Replication (TIDieR) Checklist for describing an intervention. A final report will also be prepared for The Stroke Foundation in compliance with funding requirements.

DATA SECURITY AND HANDLING

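### The only effect size defined for Aim 3 is each condition's own T1-T4 change, with no comparator, so it does not express the effect against no active maintenance that Aim 3 asks for

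*Protocol*

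**What the plan says.** Aim 3 (Protocol, Study Objectives, Aims) seeks an "initial estimate of the extent to which the two eHealth interventions maintain benefits from memory rehabilitation compared with no active maintenance". The period given for this is 18 weeks. The same section says of the four aims that "we will use the information from all four of these aims to estimate the parameters for a Phase III trial". The hypothesis there is an ordering of the three arms at the end of the study.

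Statistical Analyses, Aim 3, has two sentences. The first plans the randomised comparison: "Pairwise comparisons and linear mixed models will be used to explore between-group differences at each time point in clinical outcomes". The second defines the effect size: "The effect size of each maintenance condition, defined as the magnitude of change from T1-T4". As to its source, the sentence says that it "will be estimated with Cohen's *d* based on output from regression models". The second sentence names no comparator, no group-by-time contrast and no standardising SD.

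On timing, Memory Skills Group Sites puts T1, T2, T3 and T4 at weeks 6, 12, 18 and 24. Group Randomisation and Blinding triggers randomisation as participants complete T2. Recruitment Procedure instead ties randomisation to formal enrolment after the memory group. The No Active Maintenance section places the maintenance phase at T2-T3.

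**The concern.** Aim 3 asks a between-arm question, and the defined effect size answers a before-after one. A change within one arm does not use the randomised control. Whatever moves all arms alike (fading of the memory-group gains, practice on repeated tests, regression to the mean) is counted in it together with the intervention effect.

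The window adds a second problem. T1-T4 matches the 18 weeks of Aim 3, but the first six of those weeks come before the maintenance phase. If randomisation is at T2, the T1-T2 change also comes before allocation and cannot be an effect of the allocated arm.

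At stake is the reading of the pilot. A standardised d is the figure most easily lifted into a Phase III sample-size calculation. A within-arm d used there would be the wrong quantity, and the error can go in either direction.

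**Working it through.** The protocol gives no numerical value for this d, so there is no figure to reproduce on the point itself. The d = 0.33 under Sample size is a separate statement, with no test, alpha or power given. As a 15 v 15 comparison (two-sided 5%, assumed) it has about 14% power, so it is not reproduced as a between-arm effect. Some repeated-measures set-ups come close to 80% under assumptions that the protocol does not document. Nothing below depends on that figure.

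**1. The two quantities.** Let Δ be an arm's mean T1-T4 change divided by one common SD, positive for improvement.
- As defined: d for an arm = Δ(arm).
- As Aim 3 asks: d = Δ(eHealth arm) − Δ(no active maintenance).

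They agree only when Δ(no active maintenance) = 0.

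**2. The T1-T2 part.** Assume randomisation at T2. All arms lose 0.3 SD from T1 to T2, the control loses a further 0.3 by T4, and the booster arm holds its T2 level.
- Booster, as defined: −0.3 + 0 = −0.3.
- Control, as defined: −0.3 − 0.3 = −0.6.
- Contrast: −0.3 − (−0.6) = +0.3.

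The booster arm's own d is negative although the booster is better than control. The contrast removes the shared T1-T2 loss.

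**3. Effect on a later sample size.** Inputs are assumed: two-sided 5%, 80% power, normal approximation. Per arm, n = 2 × (1.96 + 0.8416)² / d² = 15.70 / d², rounded up.

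| Δ(eHealth) | Δ(control) | n per arm from own change | Contrast | n per arm from contrast |
|---|---|---|---|---|
| 0.5 | 0.5 | 15.70/0.25 → 63 | 0 | none: no effect |
| 0.5 | 0.2 | 63 | 0.3 | 15.70/0.09 → 175 |
| 0 | −0.33 | no finite n | 0.33 | 15.70/0.1089 → 145 |

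The own-change d makes the trial too small in the second row and hides a real contrast in the third.

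**4. Precision after the correction.** With 15 per arm (Study Synopsis, planned participants), all analysed, and d scaled by the SD of the quantity compared:
- SE(d) = √(2/15 + d²/60).
- At d = 0: √0.1333 = 0.365, so the half-width is 1.96 × 0.365 = 0.72.
- At d = 0.33: √(0.1333 + 0.0018) = 0.368, so the half-width is again 0.72.

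The corrected d is the right quantity, but it is imprecise.

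**The case against.** The strongest reply is that the sentence just before the definition plans between-group differences at every time point, T4 included. This stands. A reader might infer that Aim 3 has no randomised comparison, or that the within-arm d is its headline estimate. The protocol supports neither: the comparison is planned, and nothing ranks d above it. What remains is that the effect size itself is defined without a comparator.

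Second, d is to come from regression output, which could supply a group-by-time contrast. That is possible, but the text does not say so. The regression phrase gives the source of d, while the words before it fix what d measures. If the control counts as a maintenance condition, its change is reported too and a reader could subtract. The result is a between-arm d only if all arms share one SD, which is not stated.

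Third, the protocol does not make this d the sole input to Phase III sizing; it speaks of information from all four aims. That also stands. The sample-size illustrations show what would follow if the d were used that way. They do not describe a stated plan.

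Two further inferences should not be drawn. One is that d must be inflated by scaling to a mixed-model residual SD: the protocol does not say which SD is used, and that choice may properly sit in an SAP. The other is that a successful arm must show d near zero. That is one scenario; the Background cites a booster study with further gains after treatment.

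**Conclusion.** The point holds for the effect-size definition. As written, it yields a non-randomised quantity that does not match the comparison in Aim 3. It also includes six weeks of change before the maintenance phase. Whether those weeks also precede allocation depends on randomisation being at T2, and the two sections on that timing disagree. The lack of a comparator does not depend on the answer.

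The numerical size depends on how the control arm changes, which the documents do not give. The gap between the two versions of d equals the control arm's own standardised change: 0.2 to 0.5 SD in size across the tabulated illustrations and 0.6 in the T1-T2 example, all assumed.

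Severity is moderate. Aim 3 is a secondary objective of a 45-person pilot, its analyses are exploratory, and conduct and the primary feasibility aim are unaffected.

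**What to change.** Replace the effect-size sentence under Statistical Analyses, Aim 3, with one that:
- defines Cohen's d as the between-arm contrast, each eHealth arm minus no active maintenance, from the planned linear mixed model;
- uses one common, named SD for all arms;
- reports each d with its 95% CI;
- keeps within-arm T1-T4 change as description only.

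The contrast may be the difference in T1-T4 change or the adjusted difference at T4. The documents do not decide between them, so the sentence should name one. Given a half-width of about 0.72, Phase III planning should carry the interval forward and not rest on the point value alone.

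Separately, reconcile Recruitment Procedure with Group Randomisation and Blinding on when randomisation occurs, so that it is clear which part of T1-T4 follows allocation.

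The cost of the main change is one reworded sentence. Data, assessments and models stay the same.
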